7.2.3 Reporting a DLT

Any DLT occurring in a patient during that occur from the first dose of study treatment up to the last day of Cycle 2 (first 28 days) for the 5/9 Schedule, or the last day of Cycle 1 (first 21 days) for either 5/2 Schedule of a dose-escalation cohort must be reported to the Medical Monitor by the Investigator or designee with 24 hours of first knowledge, and to Sarah Cannon Safety Department as an SAE when appropriate (see Section [6.4](#)).

7.2.4 Determination of MTD/RP2D

The patient population used to determine the MTD/RP2D will consist of patients who have met the minimum safety evaluation requirements of the study, and/or who have experienced a DLT from the first dose of study treatment up to the last day of Cycle 2 (first 28 days) for the 5/9 Schedule, or the last day of Cycle 1 (first 21 days) for either 5/2 Schedule. Minimum safety requirements will be met if during Cycle 1 (for both 5/2 Schedules) and Cycles 1 and 2 (for the 5/9 Schedule) of treatment the patient receives a minimum of 80% of treatment doses of AZD1775, completes the safety evaluations (see [Table 2](#), [Table 3](#), and [Table 4](#)), and is observed for at least 28 days. Patients who do not meet these minimum safety evaluation and treatment requirements and who do not experience a DLT will be replaced.

Treatment dose will be considered non-tolerated and dose escalation will cease if 2 or more of 6 evaluable patients experience a DLT at a dose level.

A minimum of 12 patients will be treated at the MTD/RP2D. More than one dose level may be expanded with up to 12 patients per dose level to get further experience with the dosing schedule with AZD1775.

7.3 Effect of food on PK and safety

The preliminary effect of food on single dose pharmacokinetics (PK) of AZD1775 was assessed in approximately 12 patients on the BID schedule. At least 6 patients to be enrolled on a QD schedule will receive a single oral dose of AZD1775 with 240 mL (8 oz) of water, once in the fasted state on Cycle 1 Day 1 and once following a high-fat meal on Cycle 2 Day 1. The study will be conducted using the Food and Drug Administration (FDA) standard high-fat meal which should have a total of approximately 800 to 1000 kcal, with approximately 50% of the caloric content made up from fat (See [Appendix I](#)).

The fasted condition requires patients to fast for ≥ 10 hours before AZD1775 dosing and continue until 4 hours post-dose on Cycle 1 Day 1. Patients may have glucose (sugar tablets) and/or juice (except for juices containing grapefruit or Seville oranges) if they have signs or symptoms of hypoglycaemia after they have received AZD1775 in the fasted state. Water will be restricted from 1 hour pre-dose until 1 hour post-dose, except for the water administered with AZD1775, and any drink provided as part of the meal in the fed portion of the study.

For the fed condition, patients will be required to fast for ≥ 10 hours prior to receiving AZD1775 and then resume fasting until 4 hours post-dose, with the exception of a high-fat meal that should be eaten in the 30 minutes prior to AZD1775 being administered on Cycle 2 Day 1. The AZD1775 capsule should be administered 30 minutes after the start of meal consumption. If the meal is not completed within 30 minutes, AZD1775 may still be administered so long as 75% of the meal has been consumed within 45 minutes of the start of the meal. If the patient vomits after eating the meal but before administration of AZD1775, Investigators should contact the Medical Monitor for guidance regarding rescheduling administration of AZD1775 and subsequent AZD1775 should be administered with 240 mL (8 fluid ounces) of water. After PK assessments on Cycle 2 Day 1, patients will continue to take the drug with a regular meal for the entire cycle to assess the effect of food on safety.

After review of the PK data, if it is agreed that the data supports no clinically relevant impact of food on the PK of AZD1775 and so recommended by the SRT and AstraZeneca, the AZD1775 fasting/administration instructions in Section 7.3 may be removed or no longer observed.

7.4 Labelling

Labels will be prepared in accordance with Good Manufacturing Practice (GMP) and local regulatory guidelines. The labels will fulfil GMP Annex 13 requirements for labelling. Label text will be translated into local language.

The label will include the following information: Name of the Sponsor, Study Code, 'For Clinical Trial Use Only' and/or other market specific requirements.

Distinct labels will also allow for the AZD1775 plain and printed capsule formulations to be easily distinguishable for dispensing.

7.5 Storage

All study drugs (AZD1775) should be kept in a secure place under appropriate storage conditions. The IP label on the bottle specifies the appropriate storage.

The dispensing and retention of reserve samples of IP will be performed with the Food and Drug Administration (FDA) Code of Federal Regulations 21, Part 320 Bioavailability and Bioequivalence requirements.

7.6 Compliance

AZD1775 dosing compliance will be reviewed with the patient at the beginning of each new treatment cycle. Patients will be given a supply of study medication to take home. All patients will be required to complete a Dosing Diary, which must be returned to the clinic for review at each visit. The patient should be instructed to record each date and time the dose was taken on the dosing diary. If a dose is missed, the reason must be noted in the diary. A copy of the Dosing Diary is provided in the study reference materials.

The administration of all study drugs (AZD1775) should be recorded in the appropriate sections of the Case Report Form (CRF).

7.7 Accountability

The study drug (AZD1775) provided for this study will be used only as directed in the study protocol.

The study personnel will account for all study drugs dispensed to and returned from the patient.

Patients must return all unused medication and empty containers to the Investigator.

The study personnel at the investigational site will account for all drugs dispensed and returned and for appropriate destruction. Certificates of delivery, destruction and return must be signed.

7.8 Concomitant and other treatments

7.8.1 Permitted concomitant medications

All concomitant medications received within 14 days before the first dose of study medication and 30 days after the last dose of study medication should be recorded. Concomitant medications must be recorded in the appropriate sections of the eCRF.

Supportive Medication/Class of drug:	Usage:
Anti-emetics (excluding aprepitant [Emend] and fosaprepitant)	Premedication with anti-emetics is mandatory (excluding aprepitant [Emend] and fosaprepitant) as presented in Section 6.7.4.2
Loperamide (Imodium)	Loperamide (Imodium) is required at the first onset of diarrhoea according to ASCO guidelines (see Section 6.7.4.1).
Medications including but not limited to the following: 
 • Bisphosphonates and receptor activator of nuclear factor kappa-B ligand (RANKL) inhibitors (e.g. denosumab). • Patients requiring therapeutic warfarin or coumadin-derivative anticoagulants will be monitored with INR and Prothrombin Time (PT) as clinically indicated. • Low molecular weight heparin, rivaroxaban, or equivalent anticoagulant therapy is permitted where clinically indicated. • Patients may receive treatment with megestrol acetate when prescribed for appetite stimulation. 	Medications may be administered for maintenance of existing conditions prior to study enrolment or for a new condition that develops while on study.

7.8.2 Prohibited and restricted concomitant medications

The following treatments and the medications listed in [Appendix H](#) are prohibited or should be used with caution while on this study. Any further questions regarding concomitant treatments should be referred to the Medical Monitor.

Prohibited Medication/Class of drug:	Additional Information
Anticancer agents other than the study medications	If such agents are required for a patient, then the patient must first be withdrawn from the study.

Prohibited Medication/Class of drug:	Additional Information

Concomitant treatment with aprepitant and fosaprepitant is not allowable per protocol until further evaluation.
 
Potent or moderate inhibitors or inducers of CYP3A4, sensitive CYP3A4 substrates, and CYP3A4 substrates with a narrow therapeutic window should be avoided until additional data on drug-drug interaction becomes available.
	
No formal clinical drug interaction studies have been performed with AZD1775. An exploratory assessment of the effect of aprepitant on AZD1775 exposure in oncology patients suggests that there is a drug interaction between AZD1775 and aprepitant, as exposure to AZD1775 increased by ~60% when aprepitant was co-administered with AZD1775. The observed increase in AZD1775 exposure is likely the result of CYP3A4 inhibition by aprepitant. This increase in exposure is statistically significant. At the selected MTDs, this increase may also be of clinical importance.
 
The use of sensitive substrates of CYP3A4, such as atorvastatin, simvastatin and lovastatin are prohibited in this study. Patients should stop using these substrates > 14 days prior to initiation of study treatment (see Appendix H).

Herbal preparations/medications are not allowed throughout the study. These herbal medications include, but are not limited to: St. John's wort, kava, ephedra (ma huang), ginkgo biloba, dehydroepiandrosterone (DHEA), yohimbe, saw palmetto, and ginseng.
	
Patients should stop using these herbal medications 7 days prior to first dose of AZD1775.

Avoid concomitant use of strong CYP3A inhibitors and moderate CYP3A inhibitors.
	
See Appendix H

Grapefruit, Seville oranges and their products (e.g. juice, marmalade, etc.)
	
As grapefruit and Seville oranges are moderate inhibitors of CYP3A4, these fruits or their products should be avoided while taking AZD1775.

Restricted Medication/Class of drug:	Usage:

In vitro data suggests that AZD1775 may also be a weak reversible inhibitor of CYP2C19.
	
Caution should be exercised with concomitant administration of AZD1775 and agents that are sensitive substrates of CYP2C19, or substrates of this enzyme with narrow therapeutic range.
 
Refer to Appendix H for a list of sensitive substrates of CYP2C19, or substrates of this enzyme with narrow therapeutic range

Restricted Medication/Class of drug:	Usage:
AZD1775 has been shown to be a weak inducer of CYP1A2 in vitro with a maximum measured response between donors of 39.9% to 93.1% (at 10 µM) and 18.6% to 32.5% (at 5 µM) of the positive control omeprazole (50 µM), respectively. Given the nature of the AZD1775 dosing schedule, however, the risk of induction in the clinic is considered low.	Be initially vigilant when using substrates of CYP1A2 with a narrow therapeutic range.
Inhibitors or substrates of P-gp	In vitro studies have shown that AZD1775 may be a substrate and inhibitor for human P-glycoprotein (P-gp). Caution should be exercised when agents that are inhibitors or substrates of P-gp are administered concomitantly with AZD1775 (see Appendix H)
Substrates of Multidrug and Toxin Extruder 1 (MATE1) and MATE2K of these transporters (e.g. cimetidine, acyclovir, fexofenadine)	Caution should be used when administering substrates of MATE1 and MATE2K of these transporters (e.g. cimetidine, acyclovir, fexofenadine) as the clinical relevance of AZD1775 inhibition of the MATE pathway is not known in these compounds.
Metformin	Metformin should be used with caution. AZD1775 has been shown to be an inhibitor of MATE1 and MATE2K transporters. A drug interaction with substrates of either transporter cannot be ruled out, the most important substrate known to date being metformin.
BCRP substrates with narrow therapeutic index	Recent in vitro transporter studies have shown AZD1775 to be an inhibitor of BCRP (IC ₅₀ 5.1 µM). This finding is particularly relevant for drugs administered orally where exposure is normally limited by BCRP-mediated efflux, in particular some statins, such as rosuvastatin. Other drugs where the disposition is mediated via BCRP should be administered with caution, dose modification considered or substituted by an alternative drug.

7.8.3 Palliative radiotherapy

Patients may receive palliative radiotherapy during the study only for local pain control, and only if in the opinion of the treating Investigator the patient does not have disease progression. The radiation field cannot encompass a target lesion. Radiation to a target lesion is considered progressive disease and the patient should be removed from study treatment.

7.8.4 Other concomitant treatment

Medication other than those described above, which is considered necessary for the patient's safety and wellbeing, may be given at the discretion of the Investigator and recorded in the appropriate sections of the CRF.

8. STATISTICAL ANALYSES

8.1 Sample size estimate

The final sample size will depend on the number of DLTs and on the clinical activity observed at the different dose levels. In addition, any patients not evaluable (NE) for the Dose Escalation analysis set will be replaced in order to have the required number of patients evaluable for DLT in each dose level. The expected number of evaluable patients on the dose escalation, is 52 patients (12 on the BID dosing schedule; and up to 40 on the QD dosing schedules) assuming 12 AZD1775 dose levels (two BID dose levels and up to 10 QD dose levels for each schedule). A minimum of 12 patients (4 patients in the dose escalation plus an additional 8 patients) will be enrolled and treated at the QD MTD/RP2D. A sample size of approximately 12 patients was assessed to evaluate the effect of a high-fat meal on the PK profile of AZD1775 monotherapy during dose-escalation on the BID schedule. Of the 12 patients enrolled and treated at the QD MTD/RP2D, a minimum of 6 will be evaluated for food effect.

With the addition of 12 patients (4 patients in the dose escalation plus an additional 8 patients) patients enrolled and treated at the MTD/RP2D and approximately 6 additional patients to replace any non-evaluable patients, the total number of patients is approximately 66. However, the number of patients could be higher if more than six AZD1775 dose levels, alternative dosing schedules, or more cohorts are tested. In addition, more than one dose level may be expanded with up to 12 patients per dose level to get further experience with the dosing schedules.

8.2 Definitions of analysis sets

8.2.1 All patients set

The All Patients Set will include all patients who have signed the informed consent form (i.e. screening failures plus patients enrolled and treated). The All Patients Set will be used to list the patient accountability, AEs, and deaths on study.

8.2.2 Full analysis set

The Full Analysis Set will include all patients who have received at least one (non-zero) dose of study treatment. Patients who were replaced for assessment of DLT due to noncompliance will still be included in the Full Analysis Set, if they meet the above criteria.

8.2.3 Per protocol analysis set

The Per Protocol Analysis Set (PPS) is a subset of the Full Analysis Set (FAS) excluding subjects having an important protocol deviation. Those protocol deviations deemed to have an important impact on the analysis of study endpoints and leading to the exclusion of a subject will

be identified prior to database lock. This analysis set may be used for analyses of efficacy endpoints if appropriate.

8.2.4 Dose-limiting toxicity analysis set

The DLT Analysis Set will include all patients in the dose escalation phase who received at least 80% of the AZD1775 dose and completed the minimum safety evaluation requirements during the first 28 days (5/9 Schedule) or 21 days (either 5/2 Schedule) of treatment or who experienced a DLT during the first 28 days (5/9 Schedule) or 21 days (either 5/2 Schedule) of treatment regardless of the amount of drug received.

The patients in the DLT analysis set will be used for the determination of the MTD of AZD1775.

Refer to the SAP for additional information.

8.2.5 Pharmacokinetic analysis set

The PK Analysis Set will include all patients who receive AZD1775 and have provided at least one PK sample. If a patient has a major protocol deviation that affects the evaluability of the PK profile, then the patient will not form part of the PK Analysis Set.

Major protocol deviations include changes to the procedures that may impact the quality of the data, or any circumstances that can alter the evaluation of the PK. Examples include, but may not be limited to: vomiting following oral dosing occurring within the time frame of 2 times the median time of maximum concentration (t_{max}); sample processing errors that lead to inaccurate bioanalytical results; incomplete dose administered; incomplete PK profile collected; and/or use of disallowed concomitant medication. In the case of a major protocol deviation, affected PK data collected will be excluded from the summaries and statistical analyses, but will still be reported in the study result listings. Major deviations will be listed and summarised in the CSR.

8.3 Outcome measures for analyses

8.3.1 Tumour response

Patients will undergo regular tumour assessments until documented objective disease progression as defined by RECIST v1.1. At each restaging visit the RECIST data for a patient will be assigned a response of CR, PR, SD, or PD depending on the status of the disease compared with baseline and previous assessments (see [Appendix E](#)).

The objective response rate (ORR) is defined as the number of patients with a confirmed best objective response (OR) of CR or PR divided by the number of patients in the full analysis set. Similarly, the disease control rate (DCR) is defined as the percentage of patients in the full analysis set with a confirmed best objective response of CR or PR, or a best objective response of SD.

Progression of TL will be calculated in comparison with what the tumour burden was at a minimum (i.e., smallest sum of diameters previously recorded on study). In the absence of

progression, tumour response (CR, PR, or SD) will be calculated in comparison to the baseline tumour measurements obtained before starting treatment.

If a patient has had a tumour assessment that cannot be evaluated, then the patient will be assigned a visit response of NE (unless there is evidence of progression in which case the response will be assigned as PD).

For TL measurements, if $\leq 1/3$ of the TL sizes are missing (either not evaluable or not read, or the scan was not done) then a scaling up rule will be applied as follows:

- If $\leq 1/3$ of lesions recorded at baseline are missing, then the results will be scaled up (based on the nadir sizes) to give an estimated sum of diameters and this will be used in calculations (This is equivalent to comparing the visit sum of diameters of the non-missing lesions to the nadir sum of diameters excluding the lesions that are missing and determining at what rate the lesions are changing)
- If $> 1/3$ of lesions recorded at baseline are missing, then the TL response will be NE. However, if the sum of non-missing TL diameters would result in PD (i.e., if using a value of 0 for missing lesions, the sum of diameters has still increased by $> 20\%$ or more compared with the smallest sum of diameters on study, and has an absolute increase ≥ 5 mm) PD takes precedence over NE.

A visit response of CR will not be allowed if any of the TL data are missing.

Progression of non-target lesions is outlined below:

Visit Responses	Description
Complete Response (CR)	Disappearance of all NTLs present at baseline with all lymph nodes non-pathological in size (< 10 mm short axis).
Progressive Disease (PD)	Unequivocal progression of existing NTLs. Unequivocal progression may be due to an important progression in one lesion only or in several lesions. In all cases the progression MUST be clinically significant for the physician to consider changing (or stopping) therapy.
Non-CR/Non-PD	Persistence of one or more NTLs with no evidence of progression.

Visit Responses	Description
Not Evaluable (NE)	Only relevant when one or some of the NTLs were not assessed and, in the investigator's opinion, they are not able to provide an evaluable overall NTL assessment at this visit. Note: For patients without TLs at baseline, this is relevant if any of the NTLs were not assessed at this visit and the progression criteria have not been met.
Not Applicable (NA)	Only relevant if there are no NTLs at baseline

Details of any new lesions will also be recorded with the date of assessment. The presence of one or more new lesions is assessed as progression.

A lesion identified at a follow up assessment in an anatomical location that was not scanned at baseline is considered a new lesion and will indicate disease progression.

The finding of a new lesion should be unequivocal: i.e. not attributable to differences in scanning technique, change in imaging modality or findings thought to represent something other than tumour.

New lesions will be identified via a Yes/No tick box. The absence and presence of new lesions at each visit should be listed alongside the TL and NTL visit responses.

A new lesion indicates progression so the overall visit response will be PD irrespective of the TL and NTL response.

The overall visit response will be based upon the overall visit response as reported by the investigator, with TL, NTL and new lesion information provided and listed as supportive information.

8.3.2 Changes in tumour size

Percent changes in tumour size from baseline will also be determined for patients with measurable disease at baseline and is derived at each visit as the % change in the sum of the diameters of TLs. % change = [(post baseline TL sum – baseline TL sum) / baseline TL sum] *100.

8.3.3 Exposure to investigational product

The total time on study treatment, as well as total exposure to study treatment and the amount delivered relative to the intended amount will be summarised. The number of patients with interruption and reductions to the dose intensity of AZD1775 will also be summarised.

8.3.4 Adverse events, laboratory changes, vital signs

Safety profiles will be assessed in terms of DLTs, AEs, SAEs, laboratory data, vital signs, and ECG data that will be collected for all patients. Treatment-emergent AEs (TEAEs) are defined as any AE which initiates on or after the first day of study drug up through 30 days after study drug discontinuation.

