2.2 Secondary objectives

Secondary Objective :	Outcome Measure :
To evaluate the safety and tolerability of AZD1775 monotherapy in patients with locally advanced or metastatic solid tumours.	Treatment-emergent adverse events (TEAEs) and SAEs
To evaluate the preliminary anti-tumour activity of AZD1775 monotherapy in patients with locally advanced or metastatic solid tumours.	Best objective response (OR) to treatment will be assessed by dose level cohort according to Response Evaluation Criteria in Solid Tumours (RECIST) v1.1 (Eisenhauer et al 2009).
To evaluate the PK profile of AZD1775 monotherapy in patients with locally advanced or metastatic solid tumours.	PK parameters of AZD1775
To evaluate the preliminary effect of a high-fat meal on the PK profile of AZD1775 monotherapy in patients with locally advanced or metastatic solid tumours.	PK parameters of AZD1775
To characterise the effect of AZD1775 on QTc interval in patients with locally advanced or metastatic solid tumours.	QTc interval

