6.1 Definition of adverse events

An AE is the development of an undesirable medical condition or the deterioration of a pre-existing medical condition following or during exposure to a pharmaceutical product, whether or not considered causally related to the product. An undesirable medical condition can be symptoms (e.g., nausea, chest pain), signs (e.g., tachycardia, enlarged liver) or the abnormal results of an investigation (e.g., laboratory findings, electrocardiogram). In clinical studies, an AE can include an undesirable medical condition occurring at any time, including run-in or washout periods, even if no study treatment has been administered.

The term AE is used to include both serious and non-serious AEs.

For cases where it could be suspected that a tissue-derived medicine has been contaminated by a pathogen, information about any of the above conditions (including infection) should be collected. Any deterioration of disease targeted in the study and associated symptoms should not be regarded as an adverse event.

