6.3 Recording of adverse events

6.3.1 Time period for collection of adverse events

Adverse events will be collected throughout the study, from informed consent until 30 days after the end of the last investigational product administration.

SAEs will be recorded from the time of informed consent and should be reported to Sarah Cannon Safety Department as described in Section [6.4](#).

Following discontinuation of study treatment, SAEs considered related to study procedures should continue to be collected while patients are followed-up for disease progression.

For each patient who discontinues study treatment for a reason other than disease progression:

- Follow-up information on all ongoing AEs should continue to be collected until the survival follow-up.
- SAEs considered related to study procedures must continue to be collected and reported using standard SAE timelines and process until the end of progression follow-up (i.e., disease progression).
- All deaths must continue to be collected after progression and during the survival follow-up.

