6.3.3 Variables

The following variables will be collected for each AE;

- AE (verbatim)
- The date when the AE started and stopped
- CTCAE grade and changes in grade during the course of the AE
- Whether the AE is serious or not
- Causality rating against AZD1775 (yes or no)
- Action taken with regard to AZD1775
- Outcome

In addition, the following variables will be collected for SAEs:

- Date AE met criteria for serious AE
- Date Investigator became aware of serious AE
- Reason AE is serious
- Date of hospitalisation
- Date of discharge
- Probable cause of death
- Date of death
- Autopsy performed
- Causality assessment in relation to study procedure(s)
- Causality assessment in relation to other medication(s)
- Description of AE.

The grading scales found in the revised CTCAE Version 4.03 will be utilized for all events with an assigned CTCAE grading. For those events without assigned CTCAE grades, the recommendation in the CTCAE criteria should be utilized that converts mild, moderate, and severe events. A copy of the current CTCAE version can be downloaded from the Cancer Therapy Evaluation Program website (<http://ctep.cancer.gov>).

It is important to distinguish between serious and severe AEs. Severity is a measure of intensity whereas seriousness is defined by the criteria in Section 6.2. An AE of severe intensity need not necessarily be considered serious. For example, nausea that persists for several hours may be considered severe nausea, but not a SAE. On the other hand, a stroke that results in only a limited degree of disability may be considered a mild stroke but would be a SAE.

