7.2.2 Dose-limiting toxicity

Dose-limiting toxicities will be evaluated during the first 28 days (5/9 Schedule), or first 21 days (both 5/2 Schedules) of AZD1775 monotherapy treatment. If appropriate the DLT observation period can be extended by up to 2 weeks in case of treatment delay due to study drug-related AE. Toxicity will be graded according to the NCI CTCAE v4.03.

Patients must complete Cycle 1 (i.e. 21 days on either 5/2 schedule) or Cycle 1 and Cycle 2 (i.e. 28 days on the 5/9 schedule) safety evaluations and must receive at least 80% of the planned dose to be considered evaluable. Patients receiving less than 80% of Cycle 1 dose (21 days for the 5/2 schedule) or Cycle 1 and Cycle 2 dose (28 days for the 5/9 Schedule) will be replaced unless they experienced a DLT confirmed by the SRT.

Dose-limiting toxicities are defined as any of the following toxicities not attributable to the disease or disease-related process under investigation, that occur from the first dose of study treatment up to the last day of Cycle 2 (first 28 days) for the 5/9 Schedule, or the last day of Cycle 1 (first 21 days) for the 5/2 Schedule, and that meet at least 1 of the criteria below:

1. Haematologic toxicity \geq Grade 4 for more than 7 days including infection with febrile neutropenia
2. Grade 3 thrombocytopenia associated with Grade ≥ 2 bleeding
3. Haematologic toxicity \geq Grade 4 neutropenia or thrombocytopenia for more than 7 days, or Grade 4 Infection with febrile neutropenia, or Grade 3 neutropenic fever, or Grade 3 thrombocytopenia associated with Grade ≥ 2 bleeding.
4. Non-haematologic toxicity \geq Grade 3
5. Liver function tests (LFTs), Grade ≥ 3 total bilirubin, hepatic transaminase ALT or AST or ALP lasting >48 hours, or any change in liver functions tests consistent with Hy's Law (see [Appendix D](#).)
6. Any other toxicity that is clinically significant and/or unacceptable that does not respond to supportive care, results in a disruption of dosing schedule of more than 7 days, or is judged to be a DLT by the investigator in collaboration with the medical monitor.

A DLT excludes:

- Nausea, vomiting, or diarrhoea that responds to supportive care
- Isolated laboratory change of any grade without clinical sequelae or clinical significance
- Alopecia of any grade

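### The TEAE definition in Protocol 8.3.4 rests on onset date alone, so an AE first recorded between consent and first dose that worsens on AZD1775 drops out of the TEAE tables

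*Protocol*

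**What the plan says.** Section 2.2 names "Treatment-emergent adverse events (TEAEs) and SAEs" as the outcome measure for the secondary safety and tolerability objective. Section 8.3.4 defines a TEAE as "any AE which initiates on or after the first day of study drug up through 30 days after study drug discontinuation". Section 8.4.3 tabulates TEAEs by dose level cohort, by preferred term, system organ class and maximum CTCAE grade. Neither section has a clause for an event that began earlier and became worse.

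The collection rules allow AEs to be recorded before dosing. Section 6.3.1 states: "Adverse events will be collected throughout the study, from informed consent until 30 days after the end of the last investigational product administration". Screening can last 28 days, and 4.1 lets consent be taken before that window.

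For each AE, 6.3.3 collects "The date when the AE started and stopped" and "CTCAE grade and changes in grade during the course of the AE". No section tells sites to close a worsened AE and open a new one.

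Section 6.1 counts as an AE "the deterioration of a pre-existing medical condition following or during exposure to a pharmaceutical product". Section 7.2.2 defines DLTs as listed toxicities "that occur from the first dose of study treatment" to the end of the evaluation window. It does not require that the event was absent before dosing.

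**The concern.** A treatment-emergent table should show what appeared or became worse on the drug. A definition by onset alone shows only what appeared. An AE that begins after consent at Grade 1 and reaches Grade 3 after dosing is on-treatment toxicity in any practical sense, yet its start date fails the 8.3.4 test.

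Two consequences follow. The TEAE incidence and maximum-grade tables, which serve the secondary safety objective, can understate toxicity in a cohort. The same event can also appear in the DLT summary for a cohort and be missing from that cohort's TEAE table, leaving two safety displays in one report that do not agree. The definition also sits badly with 6.1, which treats deterioration during exposure as an AE.

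**Working it through.** The protocol gives no figure to reproduce here, so the check applies its rules to example records.

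**Rules used**
- An AE can be recorded from consent onward (6.3.1).
- Each AE has one start date, one stop date and its changes in grade (6.3.3).
- It is a TEAE only if it begins on or after the first day of drug (8.3.4).
- It can be a DLT if the qualifying toxicity occurs from first dose, within 21 days (5/2 schedules) or 28 days (5/9 schedule). Non-haematologic toxicity of Grade 3 or higher qualifies, but nausea that responds to supportive care does not (7.2.2).

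**Rules applied to three illustrative records** (not trial data; all arise after consent)

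| Record | Course | TEAE under 8.3.4? | DLT possible under 7.2.2? |
|---|---|---|---|
| A | Nausea, Grade 1 from Day -10; Grade 3 on Day 4 despite antiemetics | No: starts before Day 1 | Yes |
| B | Nausea, Grade 1 from Day 2; Grade 3 on Day 4 despite antiemetics | Yes, maximum Grade 3 | Yes |
| C | Fatigue, Grade 1 from Day -5; Grade 3 in Cycle 2 of a 5/2 schedule | No: starts before Day 1 | No: after the 21-day window |

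A and B have the same toxicity on Day 4 and differ only in when the mild phase began. Both can count towards the MTD, but only B reaches the TEAE tables. If C is non-serious, it appears in no safety summary of AEs and is seen only in the AE listing.

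**Size within a cohort.** Table 12 plans 3 to 6 patients per dosing schedule at each dose level. If one patient with such an event is omitted, the reported incidence for that event changes by 1/n:
- n = 3: 1/3 = 33 percentage points
- n = 6: 1/6 = 17 percentage points
- n = 12 (an expanded dose level): 1/12 = 8 percentage points

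**Number of patients.** This would be the number treated (about 66) × the share with an AE that began after consent and is ongoing at first dose × the share of those who worsen. The protocol gives neither share, so no estimate is made.

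**The case against.** The strongest reply is that 6.1 already covers the case: if deterioration on drug is itself an AE, that AE begins on drug and is a TEAE. This stands for conditions that predate consent. They are medical history, and their worsening can be entered as a new AE with an on-treatment start. Section 5.2.2 agrees, since it has aggravated physical findings reported as AEs. The reply is weaker for an AE already recorded before dosing, because 6.3.3 provides for grade changes within the course of that AE. Section 6.3.3 is a list of variables, however, and does not expressly forbid a new record. Exclusion is therefore the natural reading and not a certainty. If sites differ in whether they split such records, TEAE status would depend on site practice, which is also a reason to settle the wording.

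A second reply is that few AEs will be recorded before dosing. In Tables 2, 3 and 4 the AE evaluation row is blank at screening and starts on Cycle 1 Day 1. This limits the frequency but does not close the gap, because 6.3.1 starts collection at consent.

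A third reply is that the event remains visible. This is correct as far as it goes: it can appear in the DLT summary, in the SAE summary if serious, and in the All Patients Set AE listing (8.2.1). None of these replaces the TEAE incidence and maximum-grade tables.

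A reader might infer that the loss falls on symptoms common at baseline in advanced cancer. The documents do not support this, because such symptoms usually predate consent and follow the medical-history route. Anaemia is also a poor example. Under 6.3.6, deterioration in a mandated laboratory value is an AE only in limited circumstances, and 8.4.3 summarises laboratory data separately.

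**Conclusion.** The definition in 8.3.4 is wrong as written, within narrow limits. An AE first recorded between consent and first dose that increases in grade on AZD1775 is, on the natural reading, excluded from the TEAE incidence and maximum-grade tables. The protocol fixes this rule itself, so it is not a detail left to the SAP.

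The number of affected patients is unknown and may be small. Where there is one, the effect on a cohort of 3 to 6 is 17 to 33 percentage points for that event. The conclusion assumes that sites follow 6.3.3 by keeping one record per AE.

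A reader might go further and infer that dose escalation or the MTD is biased, or that worsening events are lost to safety reporting. Neither follows. DLT evaluation under 7.2.2 does not depend on TEAE status, and the DLT summary, SAE summary and AE listings are unaffected. What is at stake is a descriptive table for a secondary objective, in a study with no formal hypothesis testing. It should be corrected because the correction is easy and the table is the stated outcome measure.

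**What to change.** In 8.3.4, define a TEAE as an AE that starts, or that started before first dose and increases in CTCAE grade, on or after the first dose and up to 30 days after the last dose. For a worsened event, use the maximum post-first-dose grade in the maximum-grade table.

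The cost is one clause in the protocol and one condition in the programming. No new data are needed, since 6.3.3 already collects changes in grade. Reported TEAE incidence may be slightly higher.
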